### 3.2 Part B

Part B is a multiple ascending dose study design. Subjects will receive either PK10571 or placebo. Approximately 24 subjects will be enrolled in Part B. Subjects will be enrolled in 3 cohorts of 8 subjects each.

Gossamer Bio, Inc.

The initial dose for Part B will be determined after review of the safety and pharmacokinetic data from Part A by the Safety Review Committee.

Data from the lower dose cohort will be analyzed before deciding whether to proceed with the higher dose cohort. Alternatively, a lower dose may be administered, depending upon review of previous cohort's safety and pharmacokinetic data.

Subjects will receive one of the treatments listed in Table 3. The assigned treatment will be given either as a single daily dose (QD), or divided into two daily doses (BID), or divided into three daily doses (TID; each dose to be separated by 6 hours on a given day).

Subjects will be assigned to either active treatment or placebo in randomized fashion.

Table 3Part B: Planned Doses for Cohorts 1–3

| Cohort                 | Test Formulation (n = 6) | Placebo (n = 2) |
|------------------------|--------------------------|-----------------|
| 1                      | PK10571 initial dose     | Placebo         |
| 2                      | PK10571 mid dose*        | Placebo         |
| 3                      | PK10571 high dose*       | Placebo         |
| n = number of subjects |                          |                 |

n = number of subjects

Note: The dosing regimen will be either once daily (QD), twice daily (BID), or three times daily (TID) for 7 consecutive days. For TID dosing, each daily administration will be separated by 6 hours.

\* Alternately, Cohort 2 or 3 will receive a lower dose, depending upon safety and pharmacokinetic data from Cohort 1 or 2, respectively.

Each dose will be administered using an oral inhalation device. Meals will be the same and scheduled at approximately the same times relative to dose for each cohort, if possible. Refer to Section 5.5.1 for details regarding timing of meals for each proposed dosing regimen (QD, BID, and TID).

No water may be consumed for 1 hour prior through 1 hour after each dose, except for 60 mL of room temperature water which will be given to subjects to rinse their mouths after dosing. Subjects will swish the 60 mL of water in their mouths then spit it out.

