#### **3.4 Dose Escalation**

Dose escalation will proceed after the review of all available safety data from subjects in the preceding cohort(s) is completed, the assessment has determined that the prior dose(s) is/are safe, and escalation to the next dose level is recommended.

The following factors will be considered for determining the next incremental dose:

- 1. Observation of clinical adverse effects based on symptoms and signs;
- 2. Observed abnormalities in clinical chemistries, complete blood count (CBC), liver function tests, or coagulation tests;
- 3. Pharmacokinetic parameters: maximum concentration  $(C_{max})$  and area under the plasma versus concentration curve (AUC).
- 4. For Part A, if no adverse effects are observed at the starting dose the third dose will be the next dose will be (2 times the second dose), the fourth dose will be up to (up to two times the third dose), and the fifth dose will be up to (one and a half times the fourth dose).
- 5. For Part B, if no adverse effects are observed at the starting dose regimen (whether QD, BID, or TID), then the next dose will be a mid-dose to be determined by the Safety Review Committee, and if no adverse effects are seen at the mid-dose, then the next dose will be higher dose to be determined by the Safety Review Committee. In the event of adverse effects at a given dose the Safety Review Committee may recommend a decrease in dose for the next dosing cohort.

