## APPENDIX 1 PHARMACOKINETIC BLOOD SAMPLE COLLECTION, PROCESSING, AND SHIPMENT INSTRUCTIONS

## A. Collection and Processing

A more detailed description of plasma sample preparation requirements may be provided by the analytical laboratory. If such a description is provided, the method of sample preparation provided by the laboratory shall supersede those provided in this protocol and appropriate documentation shall be placed in the investigator site file.

|    | Processing Instructions   |
|----|---|
| 1  | Blood samples will be collected into 6 mL Vacutainer tube(s) containing K 2 -EDTA.
The time and date of collection for each sample will be recorded. Samples will be
placed on ice after collection and remain on ice throughout processing.   |
|    | PART A: Samples will be collected at 0 hour (predose) and then at 3, 10, 20, 30, 40 minutes, and 1, 2, 4, 8, 12, 24, 36, and 48 hours after study treatment administration.  |
| 2A | (Note: The predose sample will be collected within 150 minutes of dose
administration. Predose blood samples obtained from backup subjects who are
randomized into the study may exceed the predose collection window.)   |
|    | PART B: If QD dosing: Blood samples for pharmacokinetic evaluation will be
obtained prior to the first dose administration (predose) on Day 1 and Day 7, and at
the following times: Day 1 and Day 7 at 3, 10, 20, 30, and 40 minutes and 1, 2, 4, 8,
12, 24, and 36 hours after dosing; predose on Days 3-6, and on Day 8, Day 9, Day 10,
Day 14, and Day 35 (total 34 samples).   |
| 2B | If BID dosing: Blood samples for pharmacokinetic evaluation will be obtained prior
to the first dose administration (predose) on Day 1 and Day 7 and at the following
times after each dose (2 per day) on Day 1 and Day 7: 3 and 30 minutes and 2, 8, and
12 hours. Blood samples will also be collected before the first dose on Days 3-6, and
on Day 8, Day 9, Day 10, Day 14, and Day 35 (total of 30 samples).   |

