|    | If TID dosing: Blood samples for pharmacokinetic evaluation will be obtained prior
to the first dose administration (predose) on Day 1 and Day 7, and at the following
times after each dose (3 per day) on Day 1 and Day 7: 3 and 40 minutes and 6 hours.
An additional sample will be obtained on Day 2 (12 hours after the 3 rd dose on
Day 1). Blood samples will also be collected before the first dose on Days 2-6, and on
Day 8 (6 hours and 12 hours after the 3 rd dose on Day 7), Day 9, Day 10, Day 14, and
Day 35 (total of 30 samples). For multi-capsule administrations (if required to
achieve the dose), the first postdose blood collection will be performed 5 minutes
after the start of study treatment administration. |

| 3 | The predose sample on Day 1 will be collected within 150 minutes of dose
administration. Predose blood samples obtained from backup subjects who are
randomized into the study may exceed the predose collection window. |
|---|--|
| 4 | Blood samples will be centrifuged at approximately 3000 rpm for 10 minutes at 4 degrees Centigrade.  |
| 5 | The resulting plasma samples will be harvested and transferred in approximately equal aliquots into two appropriately labeled polypropylene screw-cap tubes.   |
| 6 | Samples will be placed in an upright position in a freezer at approximately -20 degrees Centigrade within 60 minutes of collection.  |
| 6 | Samples will remain frozen until assayed.  |

|                          |  | Part                 | A Sample Collect | ion Summary                            |                            |
|--------------------------|--|----------------------|------------------|--|----------------------------|
| Number
of
Subjects | Number of
time points
per period | Number
of Periods | Sample type      | Tube type                              | Number of tubes per sample |
| Up to 40                 | 14                                     | 1                    | Collection       | 6 mL K 2 EDTA
Vacutainer | 1                          |
|                          | * I                                    | 1                    | Aliquot          | 3 mL Polypropylene
screw Cap        | 2                          |

|                          |  | Part                 | B Sample Collect | ion Summary                            |                            |

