- k) Blood samples for pharmacokinetic evaluation will be obtained prior to the first dose administration (predose) on Day 1 and Day 7, and at the following times after each dose (3 per day) on Day 1 and Day 7: 3 and 40 minutes and 6 hours. An additional blood sample will be collected on Day 2 (12 hours after the 3rd dose on Day 1). Blood samples will also be collected before the first dose on Days 2-6, and on Day 8 (6 hours and 12 hours after the 3rd dose on Day 7), Day 9, Day 10, Day 14 and Day 35 (total of 30 samples). Exception: For multi-capsule administrations (if required to achieve the dose), the first postdose blood collection will be performed 5 minutes after the start of study treatment administration.

Gossamer Bio, Inc.

CONFIDENTIAL

31 Jul 2018

- 1) Urine samples for pharmacokinetic analysis will be collected on Day 1 and Day 7 (times relative to the first dose of the day) predose (spot collection) and for the first 24 hours after dosing.
- m) Subjects will remain in the research center for observation until 48 hours after the last dose (Day 9).
- n) Subjects will return to the clinical research site for a safety evaluation and PK blood draws on Days 10, 14, and 35.
- o) Subjects will be monitored for adverse events from the beginning of confinement until the end-of-study visit.

Gossamer Bio, Inc.

CONFIDENTIAL Page 71 31 Jul 2018

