6.2.10. Concentration-Time Data

PART A:

Blood samples for pharmacokinetic analysis of PK10571 will be collected at 0 hour (predose), and then at 3, 10, 20, 30, 40 minutes, and 1, 2, 4, 8, 12, 24, 36, and 48 hours after study treatment administration as specified by the protocol amendment. For two blood samples were collected at 1 and 5 minutes, instead of one blood sample at 3 minutes, prior to the protocol amendment. For and above, the 3-minute sample was collected after the protocol amendment.

PART B:

If QD dosing: Blood samples for pharmacokinetic evaluation will be obtained prior to the first dose administration (predose) on Day 1 and Day 7, and at the following times: Day 1 and Day 7 at 3, 10, 20, 30, and 40 minutes and 1, 2, 4, 8, 12, 24, and 36 hours after dosing; predose on Days 3-6, and on Day 8, Day 9, Day 10, Day 14, and Day 35 (total 34 samples).

If BID dosing: Blood samples for pharmacokinetic evaluation will be obtained prior to the first dose administration (predose) on Day 1 and Day 7, and at the following times after each dose (2 per day) on Day 1 and Day 7: 3 and 30 minutes and 2, 8, and 12 hours. Blood samples will also be collected before the first dose on Days 3-6, and on Day 8, Day 9, Day 10, Day 14, and Day 35 (total of 30 samples).

If TID dosing: Blood samples for pharmacokinetic evaluation will be obtained prior to the first dose administration (predose) on Day 1 and Day 7, and at the following times after each dose (3 per day) on Day 1 and Day 7: 3 and 40 minutes and 6 hours. An additional sample will be obtained on Day 2 (12 hours after the 3rd dose on Day 1). Blood samples will also be collected before the first dose on Days 2-6, and on Day 8 (6 hours and 12 hours after the 3rd dose on Day 7), Day 9, Day 10, Day 14, and Day 35 (total of 30 samples).

For multi-capsule administrations (if required to achieve the dose), the first postdose blood collection will be performed 5 minutes after the start of study treatment administration.

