6.2.11. PK Parameters

Concentration-time data for PK10571 will be analyzed using noncompartmental methods in PhoenixTM WinNonlin[®] (Version 6.3 or higher, Certara, L.P.)¹.

During the pharmacokinetic analysis, concentrations that were BLQ up to the time of the first quantifiable concentration will be treated as zero. Embedded (values between 2 quantifiable concentrations) and terminal BLQ concentrations will be treated as "missing". Actual sample times will be used in the pharmacokinetic analysis.

The following PK parameters will be calculated for PK10571 for single ascending dose (SAD, Part A):

Parameter	Definition
C _{max}	Maximum plasma concentration, determined directly from individual concentration-time data, reported to 3 significant figures
	C_{max} will be presented with and without weight-adjustment. Weight adjustment will be calculated as C_{max} x body weight in kg/70.
T _{max}	Time of the maximum plasma concentrations, reported to 2 decimal places
C _{last}	Last quantifiable plasma concentration determined directly from individual concentration-time data, reported to 3 significant figures

Parameter	Definition
T _{last}	Time of last quantifiable plasma concentration, reported to 3 significant figures
AUC ₀₋₂₄	Area under the plasma concentration-time curve from time-zero to 24 hours postdose, reported to 3 significant figures AUC ₀₋₂₄ will be presented with and without weight-adjustment. Weight adjustment will be calculated as AUC ₀₋₂₄ x body weight in kg/70.
AUC _{last}	Area under the plasma concentration-time curve from time-zero to the time of the last quantifiable concentration (C_{last}), as calculated by the linear trapezoidal method, reported to 3 significant figures $AUC_{last} \ will \ be \ presented \ with \ and \ without \ weight-adjustment. \ Weight \ adjustment \ will \ be \ calculated \ as \ AUC_{last} \ x \ body \ weight \ in \ kg/70.$
AUCinf	Area under the plasma concentration-time curve from the time of dosing extrapolated to infinity, reported to 3 significant figures and calculated as: $AUC_{0\text{-inf}} = AUC_{0\text{-last}} + C_{last}/\lambda z, \text{ where } \lambda z \text{ is the apparent terminal elimination rate constant calculated by linear regression of the terminal linear portion of the log concentration versus time curve AUC_{inf} \text{ will be presented with and without weight-adjustment. Weight adjustment will be calculated as } AUC_{inf} \text{ x body weight in kg/70.}$

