$\lambda_z (K_{el}, Lambda z)$	Apparent terminal elimination rate constant calculated by linear regression of the terminal linear portion of the log concentration versus time curve, reported to 3 significant figures
T _½	The observed terminal elimination half-life, reported to 3 significant figures and calculated as: $T_{1/2} = \ln(2)/\lambda_z$
CL/F	The apparent total plasma clearance after an inhaled dose, reported to 3 significant figures and calculated as:

Parameter	Definition
	CL/F=Dose/AUC _{0-inf} , where F is the bioavailability
	CL/F will be presented with and without weight-adjustment. Weight adjustment will be calculated as CL/F x 70/body weight in kg.
	The apparent volume of distribution after an inhaled dose, reported to 3 significant figures and calculated as:
V_z/F	$V_z/F=Dose/(AUC_{inf} \times \lambda_z)$, where F is the bioavailability
	Vz/F will be presented with and without weight-adjustment. Weight adjustment will be calculated as Vz/F x 70/body weight in kg.

The following PK parameters will be calculated for PK10571 for multiple ascending dose on Days 1 and 7, unless specified otherwise (MAD, Part B):

Parameter	Definition
C _{max}	Maximum plasma concentration, determined directly from individual concentration-time data, presented to 3 significant figures
	C_{max} will be presented with and without weight-adjustment. Weight adjustment will be calculated as C_{max} x body weight in kg/70.
T_{max}	Time of the maximum plasma concentrations, presented to 3 significant figures
Clast	Last quantifiable plasma concentration determined directly from individual concentration-time data, presented to 3 significant figures
T _{last}	Time of last quantifiable plasma concentration, presented to 3 significant figures
AUC ₀₋₂₄	Area under the plasma concentration-time curve for time zero to 24 hours postdose, presented to 3 significant figures

Parameter	Definition	
	AUC ₀₋₂₄ will be presented with and without weight-adjustment. Weight adjustment will be calculated as AUC ₀₋₂₄ x body weight in kg/70.	
Cavg,ss	Average concentration at steady state, calculated as AUC ₀₋₂₄ /24 h (Day 7 only), presented to 3 significant figures	
CLss/F	Apparent clearance at steady state (Day 7 only), presented to 3 significant figures and calculated as:	
	CLss/F=Total daily dose/AUC ₀₋₂₄ , where F is the bioavailability.	
	CLss/F will be presented with and without weight-adjustment. Weight adjustment will be calculated as CLss/F x 70/body weight in kg.	

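### The AUC integration rule is contradictory between protocol and SAP and unstated for Part B AUC0-24, and on the sparse TID grid the choice of rule can move AUC0-24 by tens of percent if elimination is fast

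*Protocol*

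**What the plan says.** **Sampling.** Protocol Appendix 1 row 2B, Table 11 footnote k and SAP 6.2.10 give the same TID schedule: "times after each dose (3 per day) on Day 1 and Day 7: 3 and 40 minutes and 6 hours" (5 minutes replaces 3 for multi-capsule doses). Protocol 3.2 fixes the spacing: "For TID dosing, each daily administration will be separated by 6 hours". The 24 h point for Day 1 is the Day 2 draw, 12 h after the third dose ("An additional blood sample will be collected on Day 2"). QD is sampled much more densely: "Day 1 and Day 7 at 3, 10, 20, 30, and 40 minutes and 1, 2, 4, 8, 12, 24, and 36 hours". BID has draws at 3 and 30 minutes and 2, 8 and 12 h after each dose.

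**Integration rule.**
- Protocol 8.2: log trapezoidal, stated for AUClast.
- SAP 6.2.11, Part A, AUClast row: "as calculated by the linear trapezoidal method".
- SAP 6.2.11, Part B, AUC0-24 row: no rule.
- SAP section 8: no departures from the protocol analysis.

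**Use of AUC0-24 in Part B.** It gives Cavg,ss (divided by 24 h), clearance ("CLss/F=Total daily dose/AUC"0-24) and the accumulation ratio. It also enters the Day 7 versus Day 1 ANOVA and the dose-proportionality power model (SAP 6.11). Protocol 3.4 lists Cmax and "area under the plasma versus concentration curve (AUC") among the factors for the next dose.

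**The concern.** On a falling concentration curve, a straight line between two samples lies above the true curve. The excess grows with the number of half-lives between the samples. The TID schedule leaves one long gap after each of three daily doses, so linear and log rules can give materially different areas from the same data. The QD schedule has draws at 1, 2 and 4 h, and there the choice matters little.

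Two analysts could follow these documents faithfully, one by the SAP's only named rule and one by the protocol's, and report different Part B exposures. The regimen may change between Part B cohorts, so a cohort on TID could appear to have higher daily exposure and lower clearance than one on QD, or than Part A, at the same true clearance. The bias is systematic, so more subjects would not reduce it.

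**Working it through.** **1. Check the reading of the grid against the stated sample count.** TID: 2 predose (Days 1, 7) + 3 doses x 3 draws x 2 days = 18, + 5 predose (Days 2-6) + 1 (Day 8, 12 h after dose 3) + 1 (Day 9) + 3 (Days 10, 14, 35) = 30. The plan states 30. The same reading gives the stated 34 for QD and 30 for BID.

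**2. Size of one gap by hand.** Assume instantaneous absorption and C = exp(-kt), with k = ln 2 / half-life. The gap runs from 0.667 h to 6 h, a width of 5.333 h.
- Half-life 1 h (k = 0.693): C(0.667) = 0.630 and C(6) = 0.016. Linear area = 5.333 x (0.630 + 0.016)/2 = 1.72. True area = (0.630 - 0.016)/0.693 = 0.89. The excess is 0.835, against a total area per dose of 1/k = 1.443, or 58%.
- Half-life 2 h (k = 0.347): C(0.667) = 0.794 and C(6) = 0.125. Linear area = 2.450, true area = 1.929. The excess is 0.520 out of 2.885, or 18% before carry-over from earlier doses is added.

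**3. Full 0-24 h calculation.** Inputs from the documents: nominal grids, first draw at 3 minutes, doses at 0 (QD), 0 and 12 (BID), and 0, 6 and 12 h (TID). Assumptions: first-order absorption at 60/h (absorption half-life about 0.7 minutes), linear kinetics, all samples quantifiable. Error = 100 x (AUC0-24 on the grid / exact AUC0-24 - 1).

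| Half-life | QD, linear | BID, linear | TID, linear | TID, linear-up/log-down |
|---|---|---|---|---|
| 0.5 h | +5.8% | +33.8% | +109.5% | -3.0% |
| 1 h | +6.8% | +31.6% | +58.6% | -1.6% |
| 2 h | +6.2% | +15.9% | +20.5% | -0.8% |
| 4 h | +5.3% | +5.0% | +5.8% | -0.5% |
| 6 h | +3.8% | +2.3% | +2.6% | -0.3% |
| 12 h | +1.4% | +0.5% | +0.5% | -0.2% |
| Two-phase (80% at 0.5 h, 20% at 4 h) | +5.5% | +15.0% | +41.8% | +19.1% |

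With slower absorption (20/h), TID linear error is +54.8% at 1 h and +18.2% at 2 h. The log-down error is then -6.5% and -3.4%.

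**4. Day 1 against Day 7.** The mono-exponential errors are the same on both days to within about 0.1 percentage point. In the two-phase case TID is +41.8% on Day 1 and +40.3% on Day 7, so the ratio is distorted by 1.403/1.418 = 0.99.

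**5. What passes through.** CLss/F is proportional to 1/AUC0-24. For TID it becomes 1/1.586 = 0.63 of the truth at 1 h and 1/1.205 = 0.83 at 2 h. For QD the factor is 1/1.068 = 0.94 and 1/1.062 = 0.94. Cavg,ss carries the same error as AUC0-24.

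For the power model, take one QD and one TID cohort with the total daily dose doubled (an illustration, since Part B doses are not fixed). The slope shifts by ln(1.586/1.068)/ln 2 = 0.57 at 1 h and ln(1.205/1.062)/ln 2 = 0.18 at 2 h.

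**6. Troughs below quantitation.** SAP 6.2.11 sets embedded values below quantitation to missing. If the 6 h and 12 h TID draws are lost this way, error at half-lives of 1-2 h is +57% to +173% with the linear rule and +49% to +153% with log-down, over the two absorption rates.

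**The case against.** Several objections have force.

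- **The linear rule is not prescribed for Part B.** It sits in the Part A AUClast row, and the protocol names the log method. A reader might infer that TID AUC0-24 will be overstated by 20-60%. The documents do not establish that, because under the protocol's rule the mono-exponential overstatement disappears. What stands is that they disagree and leave Part B open.
- **The half-life is unknown.** The large figures need a half-life of about 1-2 h or less, or a fast first phase. From about 4 h TID is essentially no worse than QD, and at 6 h it is slightly better.
- **TID may never be used.** A reader might also infer that TID would be picked precisely when the half-life is short. The documents set no half-life criterion; the Safety Review Committee decides on safety, including local irritation, and PK.
- **Accumulation is not at risk in the cases with quantifiable troughs.** The accumulation ratio and the Day 7 versus Day 1 ANOVA compare the same grid within subjects, so the error largely cancels.
- **Dose proportionality is affected only if Part B cohorts differ in regimen.** A constant proportional error leaves the slope unchanged. Moreover, the SAP plans no formal test of CLss/F between regimens, and AUC is only one of several escalation factors.

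These points narrow the concern. They do not remove the conflict between the documents.

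**Conclusion.** The concern holds as an unreconciled integration rule: log in protocol 8.2, linear in the SAP's Part A AUClast row, none for Part B AUC0-24, with no change declared. It matters most for TID because of the gap from 40 minutes to 6 h.

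Its numerical size is conditional on assumed kinetics. If the linear rule is carried over, TID overstatement is about 59% at a half-life of 1 h and 21% at 2 h, against 6-7% for QD. It exceeds 100% at 0.5 h and is 6% or less from 4 h upward. The quantities exposed are Cavg,ss and CLss/F. If regimens differ between cohorts, so are the Part B dose-proportionality slope and the AUC that the Safety Review Committee compares. Neither a distorted accumulation ratio nor a certain 20-60% bias follows from the documents.

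**What to change.** **Required.** In SAP 6.2.11, state that AUC in both parts, including Part B AUC0-24 for QD, BID and TID, is computed by linear-up/log-down within each dosing interval. Replace the linear wording in the Part A AUClast row. This is the workable form of the protocol's log method, since a pure log rule is undefined where a concentration is zero. It brings mono-exponential TID error to about -1% to -3% with rapid absorption, and -3% to -7% at half-lives of 1-2 h with the slower absorption tried.

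**State as limitations.** On the TID grid a two-phase decline can still leave about +20% (range in the cases tried +8% to +26%). Troughs below quantitation set to missing are not rescued by the log rule. TID AUC0-24 and CLss/F should therefore be compared with QD or Part A values with caution.

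**Cost.** A few SAP sentences and one software setting. Any AUC already computed by the linear rule would need recalculating from existing concentrations. No procedure changes for subjects.

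**Optional, not part of the fix.** A 2 h TID draw after doses 1 and 3 on Days 1 and 7 would add 4 x 6 = 24 mL, giving 353.5 + 24 = 377.5 mL, the total already planned for QD. Under log-down it changes nothing for mono-exponential decline and brings the two-phase case above to about +7% to +8%. Whether that justifies four more venous draws is a sampling trade-off for the sponsor.
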